7.6 PARTICIPANT STIPEND

Participants are compensated for completing the online questionnaires (up to \$365 in total for 16 questionnaires). If participants report 7-day PPA on the 12-, 26-, 52- and/or 104-week questionnaire, they will have the opportunity to do a biovalidation videoconference

study visit. Participants will be compensated \$50 for each biovalidation visit they complete (up to 4 biovalidation visits in total) for up to \$2000. In total, participants may earn up to \$565 over the course of the 2-year study. Compensation will be in the form of Visa or Mastercard gift cards that are mailed or emailed to their provided address. Payments will be bundled as depicted in the Informed Consent Form with participants receiving up to 6 payments over the course of the study. Bundled payments will be processed upon completion of the item(s) for which the participant is receiving payment and will take 2-3 weeks to arrive to the participant after being processed. Participants will be compensated for each questionnaire they complete, even if they do not complete all questionnaires that are included within a payment bundle.

7.7 SAMPLE SIZE AND JUSTIFICATION

As this is a pilot RCT and first assessment of Pivot compared to usual care, the study's sample size is powered to show differences in engagement, operationalized as the number of times participants open their assigned app. Previous clinical studies assessing Pivot have reported a mean of 24.2-38.7 app opens (SD range 20.8-25.9) by 90 days (data on file). In addition, Bricker et al. reported app opens comparing ACT-based smoking cessation apps (SmartQuit and iCanQuit) to QuitGuide. In one study, at 2-month follow-up, Bricker et al. reported mean (SD) app opens were 37.2 (46.1) for SmartQuit and 15.2 (13.6) for QuitGuide.[10] In a subsequent study, at 12-month follow-up, mean (SD) app opens were 37.5 (88.4) for iCanQuit and 9.9 (50.0) for QuitGuide.[11] Based on this data, we estimate mean (SD) 25 (25) app opens in the intervention arm vs. 15 (19) app opens in the control arm at 12 weeks. To detect a difference of 10 app opens or greater between Pivot and QuitGuide with 0.8 power and 0.05 alpha would require 156.7 participants, which we round up to 158. In a previous study, 272/319 (85.3%) participants completed the end-of-Pivot questionnaire at a mean (SD) 4.1 (1.4) months after enrollment. [13,14] Considering that we will assess our primary endpoint at 3 months (12 weeks), we are accordingly including an expected 15% attrition rate, with a plan to enroll up to 180 participants (up to 90 in each arm).

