	
180 adult participants (up to 90 in each arm) who report daily smoking of 5 cigarettes or more. The study will be performed remotely on an ambulatory basis. Participants will be asked to setup and use their assigned program (Pivot for intervention or QuitGuide for control). Both study arms include the option for participants to order FDA-approved nicotine replacement therapy (NRT). The study duration is 104 weeks, with the estimated active time using the program of up to 6 months and the time thereafter as follow-up. Participants will receive online questionnaires at intervals throughout the study and may undergo up to 4 videocall biovalidation study visits in which they provide breath samples using a personal carbon monoxide (CO) breath sensor, which measures CO in exhaled breath.

Data Collection	Data will be collected through participant completion of emailed online questionnaires.
Performance Variables	
Comparison between the two smoking cessation programs on:
 
 • User engagement and retention in the program • Attitudes towards quitting: desire to quit, confidence to quit, self-efficacy and difficulty to stay quit • Smoking behavior: quit attempts, change in cigarettes per day (CPD), smoking cessation via 7-and 30-day PPA (self-report and biochemically confirmed), continuous abstinence (self-report and biochemically confirmed), abstinence from all tobacco products (self-report), use of NRT • Participant feedback on the set-up, use experience, design and impact on their assigned smoking cessation program, and use of other (non-study) smoking cessation tools
Performance Endpoint and Analysis	Change from baseline measurement

Contents

1.	List of Abbreviations	7
2.	Introduction.....	8
2.1	Background	8
2.2	Study Rationale	10
2.3	Potential Risks and Benefits.....	10
2.3.1	Known Potential Risks	10
2.3.2	Known Potential Benefits.....	11
2.3.3	Risk Benefit Assessment	11
3.	Objectives	11
4.	Definitions.....	12
5.	Control – QuitGuide Plus Nicotine Replacement Therapy.....	13
5.1	QuitGuide	13
5.2	Nicotine Replacement Therapy	13
6.	Intervention - Pivot	13
6.1	Pivot Breath Sensor	13
6.1.1	Indications for Use	14
6.2	Labeling and Packaging	14
6.3	Pivot Breath Sensor Submitting a Breath Sample (Specific Steps)	14
6.4	CO Log.....	15
6.5	Pivot App.....	16
6.6	Pivot Coaching	17
6.7	Pivot Nicotine Replacement Therapy (NRT).....	17
6.8	Pivot Moderated Online Community	17
7.	Study Design and Overview	17
7.1	Study Design	17

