- Number of quit attempts at 4, 12, 26, 52, and 104 weeks (defined as answering ≥ 1 to the following question: “Since you began the study, how many times have you tried to quit smoking where you've gone at least 1 day without smoking a cigarette, even a single puff?”).
- User satisfaction with the smoking cessation program (set-up and getting started with program, recommend to friend, program design, program was useful for quitting, program helped me quit, program helped me stay quit) at 2, 3, 4, 5, 12, 26, 52 and 104 weeks
- Engagement with program, collected weekly during the first 12 weeks after enrollment:
 - Number of times app opened (self-report)
 - Number of days in which app was opened (self-report)
 - Number of weeks in which app was opened (self-report)
- Participant changes in self-efficacy at 6, 12, 26 and 52 weeks
- Participant changes in self-reported health and wellbeing at 26 and 104 weeks
- Self-reported NRT use at 4, 8, 12, 26, 52 and 104 weeks
- Use of other smoking cessation tools (apps, counseling, non-study medications, etc.) at 12, 26, 52, and 104 weeks
- Alcohol use behavior at 12, 26 and 52 weeks (Alcohol Use Disorders Identification Test-Concise or AUDIT-C screening questionnaire, 3 items) [18-20]
- Presence of depressive symptoms screening at 12, 26, and 52 weeks (Center for Epidemiological Studies Depression Scale or CES-D screening questionnaire, 10 items) [11,21-23]
- Living and social environment relating to cigarette smoking at 12, 26 and 52 weeks (live with other adults who smoke, live with romantic partner who smokes, number of close friends who smoke)
- Adverse events at 26, 52 weeks

Eligibility Criteria

The study population comprises current smokers, 21 years of age and above, who own and

regularly use a smartphone and are ready to quit smoking in the next 30 days.

Inclusion Criteria

- 21+ years of age
- Current daily cigarette smokers (at least 5 cigarettes per day) for the past 12 months
- Plans to quit smoking in the next 30 days
- Resident of the United States
- Able to read and comprehend English
- Owns and uses a smartphone compatible with the study app (iPhone 5 and above with operating system iOS 12 and above, or, Android 7.0 and above with operating system Android 7.0 and above)
- Has daily internet access on smartphone
- Comfortable downloading and using smartphone apps
- Willing to sign the Informed Consent Form

Exclusion Criteria

- Pregnancy (self-reported)

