11.2 ANALYSIS

In this pilot randomized control study, changes in measurements from baseline to intra-study to exit will be assessed. Participants will serve as their own controls and comparisons will be made to no change. One sample t-test will be used for numerical data. Fisher's Exact or Chi square tests will be used for categorical data. Analyses will be conducted to calculate mean (SD) for normally distributed variables for actual data or mean (SE) for modeled data and median (interquartile range) values in instances of non-normally distributed variables. McNemar test will be used for 2-category match-paired data. Cohen kappa statistic will be used for 3-category match-paired data. Statistical significance is set at $P < .05$. All deviations from the study protocol will be identified, recorded and analyzed.

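### Enrolling 180 with the stated 15% attrition leaves 153 participants, not the required 158, so power is about 79% and not 80% (minor)

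*Combined protocol and SAP*

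**What the plan says.** Section 7.7 of the combined protocol and SAP sizes the trial on the primary outcome, total app opens at 12 weeks. It assumes means (SDs) of 25 (25) for Pivot and 15 (19) for QuitGuide and a difference of 10 to detect. The calculation "with 0.8 power and 0.05 alpha would require 156.7 participants, which we round up to 158".

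For attrition, 7.7 relies on an earlier Pivot cohort in which "272/319 (85.3%) participants completed the end-of-Pivot questionnaire", at a mean of 4.1 months. From this it concludes: "we are accordingly including an expected 15% attrition rate, with a plan to enroll up to 180 participants (up to 90 in each arm"). The Synopsis (Study Session) gives the same ceiling: "180 adult participants (up to 90 in each arm) who report daily smoking of 5 cigarettes or more".

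Section 7.7 does not show how 180 was obtained from 158 and 15%. It also names neither the test nor whether it is one- or two-sided.

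**The concern.** A reader of 7.7 will take it that 180 enrolled, after 15% loss, still leaves the 158 needed. It does not: the section's own figures leave 153. This is the only sample-size justification in the document and it concerns the primary outcome, so anyone who reports the trial or reuses the section to plan a later one would repeat a power statement that the numbers do not quite support. What is at stake is the accuracy of a stated figure. The trial does not lose a material amount of power.

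**Working it through.** **Inputs.** From 7.7: SDs 25 and 19, difference 10, alpha 0.05, power 0.80, required total 156.7 rounded to 158, attrition 15%, enrolment up to 180. From 7.5: 1:1 allocation.

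**Reproducing the plan's figure.** The pooled SD is √((25² + 19²)/2) = √493 = 22.20.

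| Method | Total N for 80% power |
|---|---|
| Two-sided two-sample t test (non-central t) | 156.72 |
| Two-sided normal approximation | 154.8 |
| One-sided two-sample t test | 123.3 |

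The two-sided t test returns the stated 156.7, so I take it as the method behind 7.7. The choice matters little here, because 153 is also below the 154.8 of the normal approximation.

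**Attrition.**

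- Retained at full enrolment: 180 × (1 − 0.15) = 153. This is 158 − 153 = 5 short, or 156.7 − 153 = 3.7 short.
- Retained at the exact completion rate of the cited cohort: 180 × 272/319 = 153.5. Rounding 14.7% loss up to 15% therefore does not explain the gap.
- Enrolment needed: 158/0.85 = 185.9, so 186 (93 per arm). From the unrounded figure, 156.7/0.85 = 184.4, so 185.
- Largest loss that 180 can absorb: 1 − 158/180 = 12.2%, or 1 − 156.7/180 = 12.9%.
- Possible origin of 180: 156.7 × 1.15 = 180.2, whereas 158 × 1.15 = 181.7. Only the unrounded requirement multiplied by 1.15 comes close.

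**Power** (two-sided t test, SDs 25 and 19, difference 10).

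| Evaluable N | Arises from | Power |
|---|---|---|
| 158 | stated requirement | 0.803 |
| 156.7 | unrounded requirement | 0.800 |
| 153.5 | 180 enrolled, 272/319 retained | 0.792 |
| 153 | 180 enrolled, 15% lost | 0.790 |
| 144.5 | 170 enrolled, 15% lost | 0.767 |
| 136 | 160 enrolled, 15% lost | 0.741 |

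At N = 153 the difference detectable with 80% power is 10.12 app opens. The last two rows are illustrations only: 180 is a maximum, and the documents do not forecast a lower number.

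**Comparison with the uncertainty in the SD.** Section 7.7 reports Pivot SDs from 20.8 to 25.9 in earlier studies. With N = 153 and the control SD held at 19, power is 0.870 at an SD of 20.8, 0.800 at 24.5 and 0.772 at 25.9. The shortfall is smaller than this range.

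**The case against.** The strongest objection is that the point is cosmetic. One percentage point of power in a pilot is well inside the uncertainty of the planning SD, and no enrolment or conduct decision turns on it. That stands, and it is why the point is graded as minor.

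The second is that actual loss may be below 15%. The Background (section 2) reports that 288 of the same 319 participants completed a later questionnaire, at a mean of 7.2 months. That is 90.3% completion, and 180 × 288/319 = 162.5 would exceed 158. In addition, 7.3 has "Engagement with program, collected weekly during the first 12 weeks after enrollment", 8.6 sends every questionnaire to everyone whether or not earlier ones were completed, and 7.5 counts people as enrolled only once they have reported a first login. Section 11.2 defines no analysis set. So the number analysed for the primary outcome could well differ from 153. This also stands as a statement about what may happen. It does not repair 7.7, which adopts 15% for the 12-week endpoint and presents 180 as allowing for it.

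The third is that the test is inferred. Section 7.7 does not name it, and 11.2 says only "One sample t-test will be used for numerical data", which is not a between-arm comparison. The inference rests on the match to 156.7. The shortfall in numbers, 153 against 158, does not depend on it.

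**Conclusion.** The concern holds. On the figures in 7.7, full enrolment with 15% attrition yields 153 evaluable participants against a requirement of 158, and power of about 0.79 against the stated 0.80. This rests on the planning means and SDs as given, on a two-sided two-sample t test, and on reading the 15% as loss from the primary comparison, which is how 7.7 uses it. Lower attrition would narrow or close the gap; enrolment below the ceiling would widen it. The arithmetic is certain. The multiply-for-divide explanation is a plausible inference and is not needed for the conclusion. This is a correction to a stated figure and should not take priority over points that affect validity.

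**What to change.** Replace the closing statement of 7.7 with wording such as:

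> With 15% attrition, 180 enrolled gives 153 evaluable participants and about 79% power for a difference of 10 app opens (two-sided two-sample t test, SDs 25 and 19). Under these SDs, 80% power requires attrition of at most about 12–13%.

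The sponsor should confirm that this is the test used for the sample size before it is written in, since 11.2 does not name a two-sample test.

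The change costs one sentence and a slightly less favourable stated power. It needs no extra enrolment and no change to procedures or endpoints.

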7.3 STUDY OUTCOMES

- User engagement and retention in the program (number of app opens, number of days with at least one app open, number of weeks with at least one app open)
- Attitudes towards quitting: desire to quit, confidence to quit, difficulty to quit and self-efficacy
- Smoking behavior: quit attempts, change in cigarettes per day (CPD), smoking cessation via 7-and 30-day PPA (self-report and biochemically confirmed), continuous abstinence (self-report and biochemically confirmed), abstinence from all tobacco products, use of NRT
- Participant feedback on the set-up, use experience, design and impact of their assigned smoking cessation program

Outcomes include:

Primary:

- Total app opens in Pivot vs QuitGuide at 12 weeks (3 months)

Secondary:

- Change in expected difficulty in staying quit (participant self-report, scale 1-10) at 2, 4, 8, 12 weeks after enrollment
- Change in confidence levels towards quitting smoking (expected success in quitting, participant self-report, scale 1-10) at 2, 4, 8, 12 weeks after enrollment
- Desire to quit (yes/no) at 4 weeks after enrollment
- Self-reported abstinence (7-day and 30-day PPA) at 6, 8, 12, 26, 52 and 104 weeks after enrollment
- Self-reported abstinence (7-day PPA) at 2 and 4 weeks after enrollment
- Self-reported abstinence from all tobacco products at 6, 8, 12, 26, 52, and 104 weeks after

enrollment

- Biochemically confirmed abstinence at 12, 26, 52, and 104 weeks
 - To be considered biochemically abstinent:
 - Breath CO sample should be less than 10 ppm [16]
- Self-reported continuous abstinence at 26, 52 and 104 weeks, defined as a self-report of smoking no more than five cigarettes from 12 weeks after enrollment
 - 12 weeks is chosen because it allows for a full course of NRT, and it has been standard in studies that include pharmacotherapy for smoking cessation [17]
- Biochemically confirmed continuous abstinence at 26, 52, and 104 weeks, defined as a self-report of smoking no more than five cigarettes from 12 weeks after enrollment, and confirmation on all previous and present biovalidation tests:
 - Breath CO sample should be less than 10 ppm for participant to be considered abstinent [16]
- The proportion of participants who reduced their cigarettes per day (CPD) by $\geq 50\%$ compared to baseline at 4, 12, 26, 52 and 104 weeks

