8.3 ACTIVE PROGRAM USE

The participant will initiate use of their assigned program. To be considered enrolled, one must: sign the electronic informed consent form, complete the Baseline Questionnaire, and provide the date they first logged in to their assigned app. Participants may receive up to two text or email messages during the first week of the study reminding them to go into their study app and confirm they have done so. There is no pre-determined time limit on how long a participant can actively engage in their app, although it is expected most participants will complete engagement by 6 months from enrollment. For individuals enrolled in the intervention arm, coaching is available for up to 12 months from enrollment. In both arms, participants may order up to 12 weeks of NRT, in two-week increments over the first 12 months of the study. Pivot is designed to be a 12-month program. There is one possible biovalidation videocall visit at 12 weeks during this portion of the study and weekly online questionnaires at the end of weeks 1 through 12.

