Regarding use of Pivot, associated data will be accessed by study investigators with the Pivot app, including data on the use of the Pivot Breath Sensor. This app is the commercially available Pivot app. With regard to the information we will collect, we, the study sponsor, associate each logged-in user to a user ID that is a unique identifier which is generated randomly on account creation. We will periodically synchronize logs from the sensor and upload them based on this user ID only. The breath samples we collect only contain information regarding: sample ID, type, value, and time. When we upload this breath sample information, the only additional information included would be the Pivot app build information and user's breath sensor ID. Through the Pivot app, we are able to assess user app engagement characteristics such as time and duration of app openings and content accessed. We are also able to assess user inputs into the app such as cigarette logging, responses to questions asked during activities, quit dates, and the ordering of NRT. We comply with HIPAA and state this in our privacy and terms of use on our

website. As such we adhere to HIPAA's Breach Notification Rule should a data breach occur. We take careful measures to prevent a data breach including use of encryptions, secure connections, and limited access to data. We use appropriate safeguards and comply, where applicable, with 45 C.F.R. Part 164, Subpart C with respect to Electronic Protected Health Information, to prevent use or disclosure of Protected Health Information. Specifically, Pivot Health Technologies Inc. (formerly Carrot Inc.) has implemented the administrative, physical, and technical safeguards set forth in 45 C.F.R. §§ 164.308, 164.310, and 164.312 that reasonably and appropriately protect the confidentiality, integrity, and availability of any Protected Health Information that it creates, receives, maintains, or transmits.

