Regarding use of QuitGuide, we do not have access to automated data from app use. As such, use and engagement data will be self-reported on electronic CRFs via online questionnaires completed by study participants. The QuitGuide app is maintained by the U.S. Government. It is protected by various provisions of Title 18, U.S. Code. The QuitGuide app notes, "NCI complies with requirements for privacy and security established by the Office of Management and Budget (OMB), Department of Health and Human Services (DHHS), and the National Institutes of Health (NIH)."

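### The 15% attrition allowance describes one questionnaire, but the primary total appears to rest on 12 weekly self-reports; 180 enrolled leaves 153 evaluable and power 0.79, and no rule covers missed weeks

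*Combined protocol and SAP*

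**What the plan says.** Section 7.7 plans on mean (SD) app opens of 25 (25) for Pivot and 15 (19) for QuitGuide at 12 weeks, with 0.8 power and 0.05 alpha. This gives 156.7 participants, rounded up to 158. The attrition input is that in an earlier study "272/319 (85.3%) participants completed the end-of-Pivot questionnaire", at a mean of 4.1 months. The text continues: "we are accordingly including an expected 15% attrition rate, with a plan to enroll up to 180 participants".

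Section 7.3 makes total app opens at 12 weeks the primary outcome. It describes the app-open data under the secondary outcomes, as self-report: "Engagement with program, collected weekly during the first 12 weeks after enrollment". Section 8.3 gives the instrument: "weekly online questionnaires at the end of weeks 1 through 12". Section 11.1 says of the control arm: "Regarding use of QuitGuide, we do not have access to automated data from app use". For Pivot, the same section says that the sponsor can see "time and duration of app openings and content accessed". No section says which source feeds the primary total in the Pivot arm.

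Section 11.2 treats participants as their own controls, with one-sample t-tests against no change for numerical data. It names no two-sample comparison of app opens, no minimum number of weekly reports and no handling of missing weeks.

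**The concern.** The attrition input and the endpoint measure different things. The 85.3% is the share of people who answered one questionnaire, in a cohort with no QuitGuide arm. A 12-week total formed from weekly reports is complete only if 12 questionnaires were answered, so the complete share can be no larger than the share answering at week 12 and may be smaller.

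Because the plan does not say how a total is formed when weeks are missing, the choice stays open until the data are seen. Keeping only people with all 12 reports costs sample size. Adding up whatever was reported mixes questionnaire response with app use. App opens also have no pre-enrolment value, so the change-from-baseline tests in 11.2 do not supply an analysis for this outcome. It is the only outcome for which the trial is powered.

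**Working it through.** **Inputs.** Means, SDs, power, alpha, 272/319, 15% and 180 come from 7.7; 1:1 allocation from 7.5. Two-sided testing is inferred, because it reproduces the plan's figure. The documents give no weekly response rate, so every such rate below is an assumption.

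**1. The plan's figure.**
- Common SD = √((25² + 19²)/2) = √493 = 22.20; difference 10.
- Normal approximation: total N = 4 × (1.960 + 0.842)² × 493 / 10² = 154.8.
- Noncentral t: 156.72. The stated 156.7 is reproduced.

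**2. The allowance at its own value.**
- 180 × 0.85 = 153 evaluable, against 158 stated.
- Noncentrality = 10 / (22.20 × √(4/153)) = 2.79, giving power 0.790. At 158 it is 0.803.
- 158 / 0.85 = 185.9, so 186 would be needed. 180 yields 158 only if attrition is at most 1 − 158/180 = 12.2%.

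**3. Totals that require all 12 reports.** Same formula, 180 enrolled:

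| Share with all 12 | Evaluable | Power | Enrolment for 158 totals |
|---|---|---|---|
| 85% | 153 | 0.79 | 186 |
| 80% | 144 | 0.77 | 198 |
| 70% | 126 | 0.71 | 226 |
| 60% | 108 | 0.64 | 264 |
| 50% | 90 | 0.56 | 316 |

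The link from weekly response to this share depends on how misses fall. With independent misses, 85% complete needs 0.85^(1/12) = 98.7% weekly response, and 95% weekly gives 0.95^12 = 54% complete and power 0.59. Simulated at the same 95% with misses clustered within people or due to dropout, power is about 0.74 to 0.84.

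**4. Missed weeks counted as zero.** If misses are unrelated to use, the expected difference is 25r₁ − 15r₂, where r₁ and r₂ are the weekly response rates in Pivot and QuitGuide.
- Equal 85%: 21.25 − 12.75 = 8.5. Simulated power is about 0.84-0.85, because the spread shrinks too.
- 80% Pivot vs 90% QuitGuide: 20 − 13.5 = 6.5; simulated power about 0.63.
- No true difference, 90% vs 80%: a spurious 15 × 0.10 = 1.5 opens if both means are 15, or 20 × 0.10 = 2 opens if both are 20. Simulated false-positive rate about 9% and 10%.

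Simulations: gamma-Poisson counts, 90 per arm, use falling 15% a week, Welch t-test.

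**5. Is an offset for weeks reported enough?** No true difference (15 opens, SD 19), people stop reporting (average response 95% vs 70%), and use falls 25% a week. Scaling by the number of weeks reported gives about 25-28% false positives and a spurious difference of about −5.8 opens, because high early use is projected onto late weeks. Estimating each week's mean by arm and summing the 12 means, with participant-level robust SE, gives about 5%.

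**The case against.** The documents nowhere state that the primary total is the sum of 12 weekly reports, and Pivot openings are logged. That stands, so the premise is an inference. It is a strong one for QuitGuide, where no other source is described. Taking Pivot from logs and QuitGuide from recall would create a measurement difference between arms.

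The plan also does something about missing data. Section 8.6 provides reminders and sends every questionnaire regardless of earlier completion, 7.6 pays per questionnaire, and 11.1 has staff seek incomplete data. These apply to both arms and should raise response. They do not define the total for weeks that stay missing.

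A reader might infer that the trial must either fall well below 0.8 power or give a biased comparison. The documents do not support that. A large power loss needs a complete-total share well below 85%, which they neither give nor exclude; the steepest losses come from assuming independent misses. Zero-filling keeps about 0.84 power when response is equal. Bias needs unequal response, and nothing shows that it will occur. It is only plausible: the trial is open-label, and only Pivot has a coach making contact about once a week (6.6).

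**Conclusion.** The point holds in a limited form. The allowance was taken from a quantity that does not describe completeness of the primary total, and the analysis section leaves that total and its between-arm test undefined. The shortfall shown by the plan's own figures is small: 153 against 158 evaluable, power 0.79 against 0.80. If 85% answer at week 12 and a total needs all 12 reports, 0.79 is the most that this calculation can give; 0.71 and 0.56 follow from assumed completion of 70% and 50%. A false-positive rate of about 9-10% under zero-filling rests on an assumed 10-point gap in weekly response. The stronger case for acting is that these choices move both power and type I error and are cheap to settle now.

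**What to change.** 1. In 7.7, restate power as 0.79 at 153 evaluable, and show it over a range of usable-total fractions, as in the table above.
2. Name self-report as the data source in both arms for the primary analysis.
3. In 11.2, analyse the weekly counts from all randomised participants who reported at least one week. Use a negative binomial or Poisson repeated-measures model with robust SE, with terms for arm, study week, arm by week and the four stratification factors in 7.5. Report the 12-week difference and ratio. Do not rely only on an offset for the number of weeks reported, since that is biased when use declines and people stop reporting.
4. Add a sensitivity analysis over a range of lower use in unreported weeks, varied separately by arm. Pivot logs can inform the Pivot arm only; the QuitGuide range has to be assumed.

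Cost: wording changes and slightly more analysis work, with no new data. The model assumes that unreported weeks are missing at random given its terms and the reported weeks; item 4 tests how much that matters.
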